3.2 END OF STUDY AND LENGTH OF STUDY

The end of the clinical trial is defined as the date when the last patient completes the last visit (LPLV) or the date at which the last data point which is required for the statistical analysis is received, whichever is the later date. LPLV for the primary analysis is expected to occur approximately 56 weeks after the last randomized patient begins the Treatment Period.

The study ends when all patients complete the *overall 12 months safety follow-up* described below, *i.e. 4 weeks follow-up after end of treatment at week 52 plus additional 11 months safety follow-up after the Follow-up visit at week 56*.

The first patient is expected to enroll in the fourth quarter of 2016, and enrollment is anticipated to continue for approximately 15 months. The last patient is expected to complete the clinical trial approximately in the first quarter of 2019.

For each patient, the total length of the study is expected to be up to a maximum of approximately 64 weeks, including the Washout Period of 4 weeks, the Screening Period of up to 4 weeks, the Treatment Period of 52 weeks, and the Follow-up Period of 4 weeks. Patients who enter the 12-week run-in period will be included for a total length of 76 weeks.

In addition, the sponsor will offer the possibility to the patients to receive pirfenidone within the study protocol after the Follow-up visit at week 56 for up to 11 months safety follow-up. During this time, the patients should be evaluated by the treating physician approximately every three months.

3.3 RATIONALE FOR STUDY DESIGN

3.3.1 Rationale for Pirfenidone and Sildenafil Doses and Schedule

In this study, sildenafil or placebo (as a comparator) will be added to ongoing treatment of a stable dose of pirfenidone. The doses will be in accordance with the prescribing information for both treatments: pirfenidone at the approved dose for IPF of 801 mg TID (or the stable dose they have entered into the study), taken at the same times each day with food, and sildenafil at the approved dose for pulmonary arterial hypertension (PAH) of 20 mg TID, with or without food.

Patients must have been on pirfenidone treatment for at least 12 weeks before the Screening visit and the dose must have been in the range of 1602 to 2403 mg/day with demonstrated tolerability for at least 4 weeks prior to the Screening Visit and throughout the study period.

The combination treatment will continue for 12 months in this study. Compared to a 6-month observation period (used in study STEP-IPF), 12 months will likely provide a greater number of primary events for the primary analysis, thus increasing the power of the study and the clinical validity, and also provide long-term safety data on the concomitant use of pirfenidone and sildenafil in this patient population.

All participants will be managed according to the best judgment of their treating physicians as informed by current local clinical practice guidelines and the best clinical evidence for patients with IPF and PH.

3.3.2 Rationale for Patient Population

In this study, patients with advanced IPF and *risk* of Group 3 PH, will be studied. Overall, there is no robust information regarding the efficacy, tolerability and safety of the combination of sildenafil and pirfenidone in patients with IPF and there are currently no approved therapies for PH secondary to lung disease (Group 3 PH), including PH secondary to IPF.

Clinical trials in IPF, including pirfenidone trials, have generally excluded patients with advanced disease and/or PH. Patients with PH secondary to advanced IPF therefore represent a group with high unmet medical need.

The expected benefits of the pirfenidone/sildenafil combination relate to the anticipated improvements in pulmonary hemodynamics in this patient population while the progression of fibrosis and decline in lung function are attenuated by pirfenidone.

3.3.3 Rationale for Control Group and Double-Blind Design

A double-blind, randomized trial design was identified to be the most appropriate design to allow for an unbiased evaluation of sildenafil taken with pirfenidone as a treatment for the study patient population. The analysis is focused on estimating the size of the

difference in the predefined outcomes between sildenafil co-administered with pirfenidone compared to placebo and pirfenidone. Patients are randomly allocated to treatment, and patients and Investigator (and other site personnel) remain unaware of which treatment is given.

3.3.4 Rationale for Primary Endpoint Selection

The primary endpoint in this double-blind, placebo controlled study will be a composite of exercise capacity (using the 6MWT), respiratory-related (non-elective) hospitalizations and all-cause mortality. This has been expanded from the primary endpoint of only using the 6MWT in most previous studies.

3.3.5 Rationale for Biomarker Assessments

Genomic, transcriptomic and proteomic profiling of markers associated with the molecular pathways and cellular processes of lung injury and fibrosis will be measured.

Certain biomarkers may be differentially expressed in patients with advanced IPF and risk of Group 3 PH on pirfenidone treatment (e.g., possibly cytokines, chemokines and other cellular and molecular markers of lung injury and fibrosis). The blood biomarker samples that are being obtained for this study may help identify those serum and plasma proteins or blood ribonucleic acid (RNA) biomarkers related to disease progression. See Schedule of Assessments ([Appendix 1](#)) for summary of serum, plasma and blood RNA biomarker study assessments.

Genetic polymorphisms have been demonstrated to alter the development and clinical course of a number of different diseases. The purpose of assessing genetic polymorphisms in this study is to understand their potential role in the pathogenesis and associated clinical outcomes. The assessment of genetic polymorphisms will only be conducted at institutions in which such research is in accordance with institutional regulations.

Patient participation for these assessments is voluntary and declining participation will in no way influence eligibility for this study. See Schedule of Assessments ([Appendix 1](#)) for summary of serum, plasma and blood deoxyribonucleic acid (DNA) biomarker study assessments.

3.3.6 Rationale for Choice of Stratification Factors

The randomization will be stratified by availability of a previous RHC (yes/no) and by FEV1/FVC ratio below/above 0.8, to ensure an equal distribution of patients with some degree of pulmonary obstruction in both treatment groups. Stratified randomization is included as the treatment outcome may be affected by these factors.

3.3.7 Rationale for Interim Analyses

An iDMC will be established to monitor the progress of the study and ensure that the safety of patients enrolled in the study is not compromised. The iDMC may recommend

Pirfenidone and sildenafil—F. Hoffmann-La Roche Ltd
46/Protocol MA29957, Version 2

that the Sponsor stop the study for safety concerns. A detailed description of the procedures, data flow and the meeting schedule of the iDMC will be maintained in a separate iDMC Charter, by the Sponsor and the iDMC.

4. **MATERIALS AND METHODS**

4.1 **PATIENTS**

Approximately 176 patients with advanced IPF and *risk* of Group 3 PH, who have been on pirfenidone in a dose range of 1602 to 2403 mg/day with demonstrated tolerability will be enrolled in this study.

Key inclusion criteria for the study are presented in [Figure 2](#) and the eligibility criterion for *risk* of Group 3 PH (Decision Tree) is further detailed in [Figure 3](#).

Figure 2 Key Inclusion Criteria for the Study

- For the purposes of this study patients have to present with:

[figure not shown]
[figure not shown]

Figure 3 Eligibility Criterion for Risk of Group 3 PH (Decision Tree)

4.1.1 Inclusion Criteria

Patients must meet the following criteria for study entry:

1. Signed Informed Consent Form
2. Ability to comply with the study protocol in the opinion of the Investigator
3. Age 40 to 80 years (inclusive) at Screening
4. Diagnosis of IPF for at least 3 months prior to Screening
5. Confirmation of IPF diagnosis by the Investigator, in accordance with the 2011 international consensus guidelines (Raghu et al. 2011), at Screening
6. For the purposes of this study patients have to present with:
 - advanced IPF is defined as a measurable DLCO $\leq 40\%$ of predicted value at Screening;

AND

- *risk of Group 3 PH as defined by:*
 - mPAP ≥ 20 mmHg together with PAWP ≤ 15 mmHg on a previous RHC of acceptable quality.

OR

- In the absence of a previous RHC, patients with ECHO showing intermediate or high probability of Group 3 PH at screening, as defined by the 2015 ESC/ERS (peak TRV) ≥ 2.9 m/s), will be considered eligible for the study, assuming that they meet all other eligibility criteria (Galie et al 2015).

7. Prior to the start of Screening, receiving pirfenidone for at least 12 weeks, at a dose in the range of 1602 to 2403 mg/day for at least 4 weeks prior to the first Screening Visit. During this 4-week period, patients must not have experienced either a new or ongoing adverse event of NCI CTCAE (version 4.03) Grade 2 or

higher and considered by the Investigator to be related to pirfenidone, or an interruption of pirfenidone treatment of >7 days for any reason. It is expected that the dose of pirfenidone will be in the range of 1602 to 2403 mg/day throughout the study (in countries where patients will not be able to take pirfenidone for 12 weeks due to reimbursement issues, this 12-week run-in supply will be provided by the Sponsor)

8. WHO Functional Class II or III (Rubin 2004) at Screening
9. 6MWD of 100 to 450 meters at Screening
10. For women of childbearing potential: agreement to remain abstinent (refrain from heterosexual intercourse) or use a non-hormonal contraceptive method with a failure rate of <1% per year during the Treatment Period and for at least 58 days after the last dose of study treatment
 - A woman is considered to be of childbearing potential if she is post-menarcheal, has not reached a post-menopausal state (≥ 12 continuous months of amenorrhea with no identified cause other than menopause), and has not undergone surgical sterilization (removal of ovaries and/or uterus).
 - Examples of non-hormonal contraceptive methods with a failure rate of <1% per year include bilateral tubal ligation, male sterilization, hormonal contraceptives that inhibit ovulation, hormone-releasing intrauterine devices, and copper intrauterine devices.
 - The reliability of sexual abstinence should be evaluated in relation to the duration of the clinical trial and the preferred and usual lifestyle of the patient. Periodic abstinence (e.g., calendar, ovulation, symptothermal, or postovulation methods) and withdrawal are not acceptable methods of contraception.
11. For men who are not surgically sterile: agreement to remain abstinent (refrain from heterosexual intercourse) or use contraceptive measures, and agreement to refrain from donating sperm, as defined below:
 - With female partners of childbearing potential, men must remain abstinent or use a condom plus an additional contraceptive method that together result in a failure rate of <1% per year during the Treatment Period and for at least 118 days after the last dose of study treatment. Men must refrain from donating sperm during this same period.
 - With pregnant female partners, men must remain abstinent or use a condom during the treatment period and for at least 118 days after the last dose of study drug or study treatment to avoid exposing the embryo

4.1.2 Exclusion Criteria

Patients who meet any of the following criteria will be excluded from study entry:

1. History of any of the following types of PH: Group 1 (PAH); Group 1 (pulmonary veno-occlusive disease and/or pulmonary capillary hemangiomatosis); Group 2 (left-heart disease); Group 3 (due to conditions other than interstitial lung disease, including chronic obstructive pulmonary disease [COPD], sleep-disordered breathing, alveolar hypoventilation, high

altitude, or developmental abnormalities); Group 4 (chronic thromboembolic pulmonary hypertension); Group 5 (other disorders) ([Simonneau et al. 2013](#))

2. History of clinically significant cardiac disease in the opinion of the Investigator, including, but not limited to: left ventricular ejection fraction <40%, congestive heart failure Class IV New York Heart Association (NYHA), left ventricular outflow obstruction (aortic stenosis, idiopathic hypertrophic subaortic stenosis), symptomatic coronary artery disease, congestive heart failure requiring hospitalization, second- or third-degree atrioventricular block, uncontrolled or clinically significant arrhythmias; uncontrolled systemic hypertension
3. History of coexistent and clinically significant (in the opinion of the Investigator) COPD (including chronic bronchitis, emphysema), bronchiectasis, asthma, inadequately treated sleep-disordered breathing, or any clinically significant pulmonary diseases or disorders other than IPF or PH secondary to IPF
4. Hypotension (blood pressure [BP] <100 mmHg systolic or <50 mmHg diastolic), autonomic dysfunction, or conditions in which vasodilation may cause an unsafe drop in blood pressure
5. History of use of drugs and toxins known to cause PAH, including aminorex, fenfluramine, dexenfluramine, and amphetamines. (For a full list see [Galie et al, 2015](#))
6. Initiating any new cardiac or pulmonary rehabilitation program within 28 days prior to Screening and throughout the study
7. FEV1/FVC ratio <0.70 post bronchodilator at Screening
8. Any impairment other than dyspnea that limits the patient's ability to walk for at least 6 minutes or perform other study procedures
9. SpO2 saturation measured by pulse oximetry at rest <92% with ≥6 L of supplemental oxygen, at the first Screening Visit
10. Significant clinical worsening of IPF between the first Screening Visit and Day 1, in the opinion of the Investigator
11. Any serious medical condition, clinically significant abnormality on ECG at Screening or laboratory tests (hematology, serum chemistry, and urinalysis) that, in the opinion of the Investigator, may pose an additional risk in administering study treatment to the patient
12. Clinical evidence of any active infection which according to the judgment of the Investigator may interfere with study conduct, measurement of pulmonary function, or impact the course of IPF
13. Certain laboratory abnormalities or findings at Screening, including:
 - Total bilirubin above the upper limit of normal (ULN)
 - Aspartate aminotransferase (AST) or alanine aminotransferase (ALT) >1.5 × ULN
 - Alkaline phosphatase >2.0 × ULN
 - Creatinine clearance <30 mL/min, calculated using the Cockcroft-Gault formula

14. Pregnant or lactating, or intending to become pregnant during the study
15. Extent of emphysema greater than the extent of fibrotic changes (honeycombing and reticular changes) on any previous HRCT scan, in the opinion of the Investigator
16. Poorly controlled systemic hypertension (>180 mmHg systolic or >100 mmHg diastolic)
17. Use of any of the following therapies within 28 days prior to Screening:
 - Investigational therapy, defined as any drug that has not been approved for marketing for any indication in the country of the participating site
 - Any cytotoxic, immunosuppressive, cytokine modulating, or receptor antagonist agent including but not limited to azathioprine, bosentan, ambrisentan, macitentan, cyclophosphamide, cyclosporine, etanercept, iloprost, infliximab, leukotriene antagonists, methotrexate, mycophenolate mofetil, tacrolimus, montelukast, tetrathiomolybdate, corticosteroids (>15mg/day prednisolone or equivalent more than 28 days) TNF- α inhibitors, imatinib mesylate, and interferon gamma-1b
 - Any medications that are specifically used for the treatment of IPF (other than the study drug) including those listed above. N-acetylcysteine (NAC) is acceptable, provided that the dose has been stable for 28 days prior to Screening and remains unchanged throughout the study
 - Use of any medications specifically prescribed for the treatment of PH (other than study drug) after the Washout Period and throughout the study, including but not limited to endothelin receptor antagonists, prostaglandins, guanylate cyclase *stimulators* such as riociguat (see Section 4.5 of the Sildenafil SPC [[Section 1.2.2](#)]) and other phosphodiesterase inhibitors
18. Vasoactive medications including calcium channel blockers, diuretics, and vasodilators may not be added within 28 days prior to screening, and the dose of these medications must be held constant as much as possible within 7 days of Screening and throughout the study
19. History of cancer likely to result in significant disability or to require medical or surgical intervention within the next 2 years. This does not include minor surgical procedures for localized skin cancer such as basal cell carcinoma.
20. Smoked tobacco within 3 months prior to Screening or is unwilling to avoid tobacco products (cigarettes, pipe, cigars) throughout the study
21. Illicit drug or significant alcohol abuse within 12 months prior to Screening, in the Investigator's judgment
22. Concomitant treatment with strong or moderate cytochrome P450 (CYP)1A2 inhibitors or moderate CYP1A2 inducers within 4 weeks or 5 drug-elimination half-lives, whichever is longer, prior to initiation of study treatment and throughout the study
 - Strong CYP1A2 inhibitors: fluvoxamine, enoxacin

- Moderate CYP1A2 inhibitors: ciprofloxacin (if dosed at >500 mg twice daily [BID]), mexiletene, thiabendazole, oral contraceptives, phenylpropanolamine, zileuton
- Moderate CYP1A2 inducers: montelukast, phenytoin, smoking
- Inhibitors of P-glycoprotein (e.g., ketoconazole, erythromycin) or CYP3A4 (e.g., ketocconazole, itraconazole, ritonavir, erythromycin), or their inducers (e.g., rifampicin, carbamazepine, phenytoin, St John's wort).

23. Hepatic impairment, acute or chronic hepatitis or known liver cirrhosis
24. Severe renal impairment including end-stage renal disease requiring dialysis
25. Poorly controlled diabetes mellitus requiring insulin therapy
26. Known HIV infection
27. ECG with a heart-rate-corrected QT interval (corrected using Fridericia's formula [QTcF]) ≥ 500 ms at Screening, or a family or personal history of long QT syndrome.

Additional Exclusion Criteria Based on Pirfenidone Reference Safety Information

1. Any contraindication to pirfenidone, including known hypersensitivity to the active substance or any excipient
2. Pirfenidone should not be used in patients with a history of angioedema due to pirfenidone
3. Concomitant use of fluvoxamine

Additional Exclusion Criteria Based on Sildenafil Reference Safety Information

1. Any contraindication to sildenafil, including known hypersensitivity to the active substance or any excipient;
2. Co-administration with nitric oxide donors (such as amyl nitrite) or organic nitrates (nitroglycerin) in any form (potentiates the hypotensive effects)
3. The co-administration of PDE5 inhibitors, including Viagra, with guanylate cyclase stimulators, such as riociguat, is contraindicated as it may potentially lead to symptomatic hypotension
4. Combination with the most potent of the CYP3A4 inhibitors (e.g., ketoconazole, itraconazole, ritonavir)
5. A loss of vision in one eye because of non-arteritic anterior ischaemic optic neuropathy (NAION), regardless of whether this episode was in connection or not with previous PDE5 inhibitor exposure.
6. Recent history of stroke or myocardial infarction
7. Known hereditary degenerative retinal disorders such as retinitis pigmentosa
8. Patients with anatomical deformation of the penis (such as angulation, cavernosal fibrosis or Peyronie's disease), or in patients who have conditions

- which may predispose them to priapism (such as sickle cell anemia, multiple myeloma or leukemia)
- 9. Patients with bleeding disorders or active peptic ulceration.
- 10. Patients with rare hereditary problems of galactose intolerance, the Lapp lactase deficiency or glucose-galactose malabsorption

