Pirfenidone pharmacokinetics (PK) have been characterized in humans. After oral administration of a single dose of 801 mg (i.e., 1 of the 3 doses taken daily to reach the approved 2403 mg/day) in healthy, fed adults, pirfenidone is absorbed relatively slowly, with a mean peak plasma concentration of 7.87 μ g/mL approximately 3 to 4 h after ingestion. The area under the concentration-time curve from time zero to infinity (AUC_{0- ∞}) and the maximum concentration (C_{max}) of pirfenidone when administered after a meal was significantly lower (using Food and Drug Administration [FDA] bioequivalence criteria) than when pirfenidone was given while fasting. A population PK analysis indicated that pirfenidone PK in IPF patients are similar to those in healthy subjects.

Clinical studies have shown pirfenidone is primarily metabolized by cytochrome (CYP) 1A2 with contribution from multiple other CYPs. The most clinically significant factors that can influence pirfenidone PK are moderate to severe hepatic impairment (moderate liver cirrhosis [Child-Pugh Class B]) and co-administration of moderate to strong CYP1A2 inhibitors or inducers (including smoking), detailed at the following website: <http://www.medicine.iupui.edu/clinpharm/ddis/main-table/>

Three randomized, double-blind, placebo-controlled Phase 3 studies evaluating pirfenidone in patients with IPF have been conducted: Studies PIPF-004 and PIPF-006, (CAPACITY) completed in 2008 ([Noble et al. 2011](#)) and Study PIPF-016 (ASCEND) completed in 2014 ([King et al. 2014](#)). Studies PIPF-004 and PIPF-006 evaluated the efficacy and safety of treatment with pirfenidone for a minimum of 72 weeks; the PIPF-016 evaluated treatment with pirfenidone for 52 weeks. A total of 1247 patients were included in the pooled Phase 3 analysis (Studies PIPF-004/006/016), of these 623 were randomized to treatment with pirfenidone (2403 mg/day) and 624 were randomized to treatment with placebo ([Noble et al. 2015](#)).

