4.4.1 Permitted Therapy

All medical therapies necessary to treat the patient's comorbidities and which are not listed below in [Section 4.4.2](#) are permitted in this study.

Patients of childbearing potential, who use oral contraceptives, hormone-replacement therapy, or other maintenance therapy should continue their use.

Sildenafil and PDE5 inhibitors that are used only intermittently for erectile dysfunction are permitted in the 28 days before the start of Screening but not after Screening and the remainder of the study. PDE5 inhibitors other than sildenafil used intermittently for erectile dysfunction are not allowed throughout the study.

Small steroid doses (e.g., 15 mg prednisolone or equivalent) are acceptable during the study. N-acetylcysteine is also acceptable during the study.

Corticosteroids may be used at the discretion of the investigator, without dose restriction, for a period of up to 28 days in patients experiencing an episode of acute IPF exacerbation. The study drug should be continued during this time, if possible.

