4.4.2 Prohibited Therapy

Use of the following therapies is prohibited during the study treatment:

- Any cytotoxic, immunosuppressive, cytokine-modulating, or receptor-antagonist agent, including but not limited to azathioprine, bosentan, ambrisentan, cyclophosphamide, cyclosporine, etanercept, iloprost, infliximab, leukotriene antagonists, methotrexate, high dose of corticosteroids (>15mg/day prednisolone or equivalent for more than 28 days), mycophenolate mofetil, tacrolimus, montelukast, tetrathiomolybdate, TNF- α inhibitors, imatinib mesylate, Interferon gamma-1b and tyrosine kinase inhibitors

- Strong CYP1A2 inhibitors (e.g., fluvoxamine, enoxacin), inhibitors of P-glycoprotein (e.g., ketoconazole, erythromycin) or CYP3A4 (e.g., ketoconazole, erythromycin), or their inducers (e.g., rifampicin, carbamazepine, phenytoin, phenytoin, St John's wort)
- Medications that are specifically being used for the treatment of IPF, including but not limited to angiotensin converting enzyme inhibitors, colchicine, heparin, warfarin, and HMG-CoA reductase inhibitors. These drugs may be used if given for a non-IPF indication if there is no clinically acceptable alternative therapy for the same indication
- Use of any medications specifically prescribed for the treatment of pulmonary hypertension (other than study drug) after the Washout Period and throughout the study, including but not limited to endothelin receptor antagonists, prostaglandins, guanylate cyclase *stimulators* such as riociguat and other phosphodiesterase inhibitors
- Any investigational therapy in a clinical study
- Because moderate inhibitors of CYP1A2 (e.g., ciprofloxacin) increase systemic exposure of pirfenidone (Esbriet® US label 2014), if ciprofloxacin is administered it should be limited to 250 or 500 mg daily (QD), and the patient should be monitored close
- Nitric oxide donors (such as amyl nitrite) or nitrates in any form due to the hypotensive effects of nitrates

The above lists of medications are not necessarily comprehensive. Thus, the Investigator should consult the prescribing information for any concomitant medication as well as the Internet references provided below when determining whether a certain medication is metabolized by or strongly inhibits or induces CYP1A2 or CYP3A4. In addition, the Investigator should contact the Medical Monitor if questions arise regarding medications not listed above.

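### Contraception and CYP1A2 wording is misaligned: inclusion 10 calls hormonal methods non-hormonal, exclusion 22 and Section 4.4.1 conflict on oral contraceptives, and Section 4.4.2 does not repeat the bar on moderate inhibitors (minor)

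*Protocol*

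**What the plan says.** **Exclusion 22 (Section 4.1.2)** bars strong and moderate CYP1A2 inhibitors for 4 weeks or five elimination half-lives, "whichever is longer, prior to initiation of study treatment and throughout the study". Its list of moderate ones reads "Moderate CYP1A2 inhibitors: ciprofloxacin (if dosed at >500 mg twice daily [BID]), mexiletene, thiabendazole, oral contraceptives, phenylpropanolamine, zileuton".

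**Inclusion 10 (Section 4.1.1) and the synopsis** ask women of childbearing potential to abstain or use a non-hormonal method with a failure rate below 1% per year. Five examples follow: tubal ligation, male sterilization, ovulation-inhibiting hormonal contraceptives, hormone-releasing intrauterine devices and copper devices.

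**Section 4.4.1** says: "Patients of childbearing potential, who use oral contraceptives, hormone-replacement therapy, or other maintenance therapy should continue their use". It also permits "All medical therapies necessary to treat the patient's comorbidities and which are not listed below in" Section 4.4.2.

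**Section 4.4.2** prohibits on study "Strong CYP1A2 inhibitors (e.g., fluvoxamine, enoxacin), inhibitors of P-glycoprotein (e.g., ketoconazole, erythromycin) or CYP3A4". A later item begins "Because moderate inhibitors of CYP1A2 (e.g., ciprofloxacin) increase systemic exposure of pirfenidone" and then limits the dose of ciprofloxacin, the only moderate inhibitor it names as such. Its closing paragraph says the lists may be incomplete. It sends investigators to the prescribing information and web references to see whether a drug strongly inhibits CYP1A2, and to the Medical Monitor if questions arise.

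**Section 1.2.1** counts both moderate and strong CYP1A2 inhibitors among the clinically most important influences on pirfenidone pharmacokinetics.

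**The concern.** These are working rules for sites, and they do not agree. A woman who takes an oral contraceptive is told by one section that she may not and by another that she should continue. A woman choosing a method is told it must be non-hormonal and is then offered two hormonal ones. The first of these is not limited to non-oral forms, so inclusion 10 can be read as accepting a method that exclusion 22 bars. Pregnancy is both an exclusion and a reason to stop treatment, so the instruction should be right even if it applies to one patient.

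For concomitant drugs, the protocol itself says that moderate CYP1A2 inhibitors raise pirfenidone exposure and bars them on study. The section a site would open when a new prescription is proposed does not carry that bar.

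**Working it through.** The plan gives no figure on this point, so the check is a comparison of the texts, followed by a rough patient count on stated assumptions.

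**1. Contraceptive examples.** Of the five examples in inclusion 10, two are hormonal: ovulation-inhibiting hormonal contraceptives and hormone-releasing intrauterine devices. So 2 of 5 contradict the requirement they illustrate. The synopsis repeats the same list.

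**2. Oral contraceptives, followed through the trial.**

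| Stage | Text | Instruction |
|---|---|---|
| Before treatment | Exclusion 22 | Not allowed within 4 weeks or five half-lives |
| Washout | Section 3.1 | Prohibited drugs stopped for 28 days, then screening |
| On study | Exclusion 22 | Still not allowed |
| On study | Section 4.4.1 | Users should continue |

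Exclusion 22 does not make Section 4.4.1 empty. A user could stop, wash out and enrol, and her site would then meet the Section 4.4.1 sentence. From that point the two texts cannot both be followed.

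**3. Moderate CYP1A2 inhibitors.** Exclusion 22 names six: ciprofloxacin above a dose threshold, mexiletene, thiabendazole, oral contraceptives, phenylpropanolamine and zileuton. Section 4.4.2 names one of the six, ciprofloxacin. Section 4.4.1 deals with oral contraceptives, in the opposite direction to exclusion 22. That leaves 6 − 1 − 1 = 4 drugs on which Sections 4.4.1 and 4.4.2 are silent by name. A site that reads only those two sections finds that comorbidity treatments not listed in 4.4.2 are permitted, and that the test for unlisted drugs is strong inhibition. It could find a drug to be a moderate inhibitor and conclude that it is allowed, although exclusion 22 says otherwise.

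**4. Patients reached.** The protocol gives N = 176 and ages 40 to 80, but no sex split and no contraceptive use. Assumed: 20–30% women, 2–10% of them of childbearing potential, 0–30% of those on an oral contraceptive.

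- Women of childbearing potential, low: 176 × 0.20 × 0.02 = 0.70
- Women of childbearing potential, high: 176 × 0.30 × 0.10 = 5.28
- Oral-contraceptive users among them, low: 0.70 × 0 = 0
- Oral-contraceptive users among them, high: 5.28 × 0.30 = 1.58

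No count can be given for step 3, because the protocol has no data on use of the other drugs.

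**The case against.** The contraception text has no good defence beyond the small number of women affected. That is conceded, and it is why the point is minor.

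The defence on CYP1A2 inhibitors is stronger. The bar is in force throughout the study under exclusion 22. Section 4.4.2 warns about moderate inhibitors as a group, with ciprofloxacin only as an example, and says its lists are not complete. Section 4.3.2.5 asks for monitoring in line with the labels of all drugs used. Counting one of six drugs therefore measures omissions from a list that does not claim to be full. All of this stands. A reader might infer that the protocol allows moderate inhibitors on study; it does not. What remains is narrower: nothing in Section 4.4.2 says that moderate inhibitors are barred, its check is worded for strong ones, and Section 4.4.1 makes absence from 4.4.2 a ground for permission.

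A reader might also infer a contradiction over ciprofloxacin. Exclusion 22 bars it above 500 mg twice daily (2 × 500 = 1000 mg/day), while Section 4.4.2 caps it at 250 or 500 mg once daily. There is no contradiction: a site that keeps to the Section 4.4.2 cap meets both rules.

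**Conclusion.** The protocol is wrong as written on contraception. Inclusion 10 and the synopsis contradict themselves in 2 of 5 examples, and exclusion 22 and Section 4.4.1 give opposite instructions on oral contraceptives. On moderate CYP1A2 inhibitors, Section 4.4.2 is out of line with exclusion 22 in the place sites are likely to look, but the rule itself exists.

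The size is small: roughly 1 to 5 women for the inclusion 10 wording, and between none and 2 for the oral-contraceptive conflict. Both counts rest wholly on the assumed shares above. The text comparison does not depend on them.

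Nor do the documents support a reading that this threatens the trial's result. Pirfenidone is background therapy in both arms, few patients are likely to be involved, and nothing here touches the endpoint, the test or the sample size. It is a safety-wording correction that should be made.

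**What to change.** **Contraception**

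- Delete oral contraceptives from the Section 4.4.1 sentence, and require a replacement method to be in place before an oral contraceptive is stopped.
- Then either remove both hormonal examples from inclusion 10 and the synopsis or, if the clinical team accepts non-oral hormonal methods, delete the word *non-hormonal* there and limit the hormonal examples to non-oral forms.
- If the team would rather allow oral contraceptives, keep the Section 4.4.1 sentence, delete *non-hormonal*, and exempt oral contraceptives expressly in both exclusion 22 and Section 4.4.2. Striking them from the exclusion 22 list alone would leave its class bar in force.

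**Moderate CYP1A2 inhibitors**

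- Have Section 4.4.2 cite exclusion 22 or list its moderate inhibitors.
- In the closing paragraph of Section 4.4.2, change *strongly inhibits* to *strongly or moderately inhibits*.
- Have the clinical team confirm how Section 4.5.16 applies, since it requires treatment to stop when a prohibited concomitant drug is used.

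Leave the ciprofloxacin limit in Section 4.4.2 as it is, including the once-daily condition.

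**Cost:** a wording amendment to Sections 4.1.1, 4.4.1 and 4.4.2 and the synopsis (and 4.1.2 if oral contraceptives are allowed), a check of the contraception text in the consent form, and a letter to sites. Two clinical decisions are needed, on hormonal methods and on the stop rule. Allowing oral contraceptives would be a small eligibility change. Analysis and sample size do not change.
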